5.6. Childbearing Potential and Methods of Contraception

For female patients, data related to childbearing potential and reproductive status is collected at the screening and FU visits (see Table 1 and Table 2 of the study protocol). For female and male

patients, methods of contraception is collected at the screening visit. All of the childbearing and methods of contraception data will be presented in listings.

5.7. Study Protocol Deviations

Important protocol deviations as reported in [REDACTED] (external vendor) Clinical Trial Management System (CTMS) will be summarized overall and for each category using descriptive statistics. All protocol deviations will also be included in a listing.

Protocol deviations pertaining to study conduct due to emergency situations (eg, COVID-19 outbreaks), including implemented contingency measures and their impact (eg, patient discontinuation from treatment with IMP and/or study, alternative procedures used to collect critical safety and/or efficacy data, etc.), will be described in the appropriate sections of the CSR, as applicable.

In addition, it should be noted that data pertaining to protocol deviations including potential ICEs will be reviewed in a planned Statistical Data Review meeting prior to unblinding of the treatment codes. Important protocol deviations and ICEs determined by the study team in this meeting will be subsequently documented in the Statistical Data Review meeting minutes.

5.8. Hospitalization and Re-hospitalization

Hospitalization/re-hospitalization data is collected during Period 1. Patients discharge status, discharge criteria, time duration (in days) of hospitalization from first IMP dose, and whether patients were re-hospitalized will be summarized using descriptive statistics. Hospitalization will include the full extent of its duration, i.e. if hospitalization continued to period 2 then the duration of hospitalization will include the time in period 2 as well.

6. EFFICACY ANALYSIS

6.1. General

Per protocol, the efficacy analysis set (Section 3.2) was planned to be used for the primary efficacy estimand and other efficacy type-I error controlled endpoint analyses. The full analysis set (Section 3.1) will be used for exploratory efficacy analyses and supplementary analyses, unless otherwise specified. However, since the option to enroll patients into Period 1 randomization following the cessation of the enrollment to placebo (Section 6.9.3, the Study Protocol) was not exercised the efficacy and full analysis sets are indistinguishable. Thus, all analyses will be conducted on the full analysis set.

Summaries will be presented for Period 1 and for the integrated study periods (including randomization through Period 2), but only data from Period 1 will be used for the primary and secondary efficacy analysis.

6.2. Primary Efficacy Endpoint and Analysis

The primary estimand is defined in Section 1.2.1. Three pairwise comparisons of low (318mg q1m), medium (425mg q1m), or high dose (531mg q1m) of TV-44749 compared to placebo will be evaluated according to the randomization assignment in Period 1, regardless of the actual treatment received.

6.2.1. Definition of Endpoint

The primary efficacy endpoint is change from baseline to week 8 in the PANSS total score. This instrument is a 30-item scale used to identify the presence and severity of psychopathology symptoms related to Schizophrenia. Each of the items is scored from 1 (absence of symptoms) to 7 (severe symptoms presentation). The sum of the 30 items, provides the PANSS total scores, which ranges from 30 to 210.

6.2.2. Estimand

The primary efficacy estimand is described in Section 1.2.1 in accordance with the estimand framework detailed in ICH E9R1. As noted in that section, intercurrent events will be handled using the hypothetical or hypothetical-treatment policy approach, as appropriate.

6.2.3. Multiple Imputation Methods

For ICEs using the hypothetical strategy (Section 1.2.1), data collected after the ICE will be handled as analysis missing, and a multiple imputation method will be used to handle this missing data.

For ICEs of early discontinuation of randomized treatment due to lack of efficacy/disease progression, or use of prohibited antipsychotic medication that are not part of the management of patients with schizophrenia (see Section 1.2.1), imputations will be performed assuming Copy Increment from Reference (CIR) in order to estimate what would have happened if patients who discontinued early had remained in the study and had a similar ('trend') slope to patients on placebo group from the time of ICE onward (White et al 2019).

For ICEs of early discontinuation of randomized treatment due to a reason that is not lack of efficacy, imputations will be performed using MAR, i.e., assuming that the clinical effect in these patients is similar to those in the same treatment arm that did not experience an ICE during the study.

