3.2. Estimand

3.2.1. Primary Estimand

For the primary efficacy objective, the following estimand attributes will be employed:

- a. **Treatment:** the treatment of low, medium, or high dose of TV-44749 compared to placebo, separately, will be evaluated according to the randomization assignment at Period 1.
- b. **Population:** all randomized adult patients who have a confirmed diagnosis of schizophrenia, present with acute exacerbation of disease, and are eligible for olanzapine treatment.
- c. **Endpoint:** change from baseline to week 8 in the PANSS total score while (as if) patients did not withdraw from randomized treatment or use prohibited antipsychotic medications.
- d. **Population-level summary:** Rubin's rule-derived least squares means of the difference in the change from baseline to week 8 between treatment groups according to the randomization assignment, regardless of the treatment actually received.

Any data collected after the intercurrent event (ICE) of taking prohibited antipsychotic medications or early termination (ET) due to insufficient clinical response (lack of efficacy) will be regarded as patients not reaching the optimal treatment effect (ie, missing not at random [MNAR]). ICE of early discontinuation for other reasons will be regarded as if the patient fully complied and completed the study (assuming missing at random [MAR]); see [Table 4](#) for further details on the classification and handling of ICEs. This complies with the hypothetical approach.

Table 4: Classification of Intercurrent Events

Intercurrent Event	Strategy	Analysis
Early discontinuation due to: Lack of efficacy Prohibited antipsychotic Disease progression	Hypothetical	Measurements after ICE will be imputed using reference-based imputation (assuming MNAR)
Self-administered prohibited antipsychotics Suicide	Hypothetical	Measurements after ICE will be imputed using reference-based imputation (assuming MNAR)

Table 4: Classification of Intercurrent Events (Continued)

Intercurrent Event	Strategy	Analysis
Early discontinuation due to other reasons (including due to adverse event)	Hypothetical	Measurements after ICE will be imputed based on randomized treatment group (assuming MAR)
Allowed concomitant medications Adverse event that did not lead to discontinuation Use of prohibited medications that are not antipsychotic Injection site reaction Out of window safety assessments	Treatment policy	Measurements after ICE will be included in analysis

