APPENDIX B. MULTIPLE IMPUTATION DETAILS**Primary Analysis****Data preparation**

Intercurrent events (ICEs) are defined in [Table 1](#) (Section 1.2.1). Visits where an ICE occurred will be labelled with the appropriate ICE type:

USUBJID	TRT01P	AVISITN	AVISIT	ADY	AVAL	CNSRDT	EVNTDESC
██████████	Placebo	4		Visit 4/ Week 1		██████████	
██████████	Placebo	5	██████████	Visit 5/ Week 2	2	██████████	Prohibited antipsychotic
██████████	Placebo	6		Visit 6/ Week 3	2	██████████	Prohibited antipsychotic
██████████	Placebo	7		Visit 7/ Week 4	2	██████████	Prohibited antipsychotic
██████████	Placebo	8		Visit 8/ Week 5	2	██████████	Prohibited antipsychotic
██████████	Placebo	9		Visit 9/ Week 6	2	██████████	Prohibited antipsychotic
██████████	Placebo	10		Visit 10/ Week 7	2	██████████	Prohibited antipsychotic
██████████	Placebo	11		Visit 11/ Week 8	2	██████████	Prohibited antipsychotic

The classification of intercurrent events (ICEs) will be performed as follows:

Event	CNSR	EVNTDESC
Early termination from randomized treatment due to "Lack of Efficacy" or an Adverse Event of "Exacerbation of schizophrenia"	1	ET due to lack of efficacy
An oral antipsychotic use was documented in the CRF (Concomitant Medication or Protocol Deviations) and reviewed in a blinded manner in the statistical data review meeting and does not meet the conditions in Section 1.2.1	2	Prohibited antipsychotic
Early termination from randomized treatment due to other reasons	3	ET due to other reasons

Multiple Imputation Method

[figure not shown]
Parameter Estimation Model

Imputation of ICE data under MAR

Imputation of ICE data under MNAR

[figure not shown]

Analysis model

[figure not shown]
Tipping Point Analysis (Two dimensional)

Tipping Point Analysis (One dimensional)

[figure not shown]
[figure not shown]
[figure not shown]
[figure not shown]
[figure not shown]
The above process will be repeated, but the delta value for the placebo group will be held at zero. The range of delta values and increments may be adjusted post hoc depending on the observed treatment effect in order to most effectively characterize the “tipping point”.

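### The SAP's visible rules for coding intercurrent events handle suicide, non-oral antipsychotic use and disease progression differently from Protocol Table 4 or from SAP Table 1

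*SAP*

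**What the plan says.** Protocol 3.2.1, Table 4 has two rows handled by reference-based imputation under MNAR. One reads "Early discontinuation due to: Lack of efficacy Prohibited antipsychotic Disease progression". The other reads "Self-administered prohibited antipsychotics Suicide", which is two entries run together by the table layout. Discontinuation for any other reason, adverse events included, is MAR. Protocol 10.5.6.1(b) describes the MAR class as excluding both lack of efficacy and death.

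SAP Table 1 gives CIR to discontinuation for lack of efficacy or disease progression, and to prohibited antipsychotic use outside a defined short-term oral exception. It gives MAR to discontinuation for other reasons. SAP 6.2.3 repeats the CIR group, beginning "For ICEs of early discontinuation of randomized treatment due to lack of efficacy/disease progression, or use of prohibited antipsychotic medication", and then states: "For ICEs of early discontinuation of randomized treatment due to a reason that is not lack of efficacy, imputations will be performed using MAR".

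Appendix B turns this into three codes, introduced by "The classification of intercurrent events (ICEs) will be performed as follows":

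- CNSR=1: "Early termination from randomized treatment due to 'Lack of Efficacy' or an Adverse Event of 'Exacerbation of schizophrenia".
- CNSR=2: "An oral antipsychotic use was documented in the CRF (Concomitant Medication or Protocol Deviations", for use that falls outside the conditions of SAP 1.2.1.
- CNSR=3: "Early termination from randomized treatment due to other reasons".

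SAP 1.2.1 adds that antipsychotic use after early termination is not an intercurrent event. SAP 17.1 declares one change to the primary estimand, the short-term oral exception. The SAP Introduction gives the SAP precedence over the protocol.

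**The concern.** These rules decide which patients are imputed on the placebo increment and which on their own arm's trajectory in the primary analysis. The key secondary endpoints rely on the same SAP Table 1. Because the SAP prevails, an event it does not name goes wherever its residual rule sends it, whatever the protocol's estimand says. If that differs from Protocol Table 4 without being declared, the analysis estimates something slightly different from the protocol's estimand. If the SAP's own table, text and codes disagree, the study team has to choose between MAR and CIR when a case turns up.

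**Working it through.** **Text comparison.** The visible part of Appendix B does not link codes to imputation methods, so the link is inferred from Table 1.

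| Event | Protocol | SAP Table 1 | SAP 6.2.3 (visible) | Appendix B |
|---|---|---|---|---|
| Suicide | Reference-based MNAR (Table 4) | No row; residual MAR | Not named; caught by MAR sentence | No code; CNSR=3 by default |
| Non-oral prohibited antipsychotic before termination | MNAR (Table 4, 10.5.6.1(a)) | CIR | CIR | CNSR=2 limited to oral; no code |
| Disease progression | MNAR (Table 4) | CIR | CIR by name, then literally MAR in the next sentence | CNSR=1 only if recorded as lack of efficacy or an exacerbation adverse event |
| Non-suicide death | Fits the MAR row of Table 4; excluded from MAR in 10.5.6.1(b) | Residual MAR | Protocol's exclusion of death is gone | CNSR=3 by default |
| Discontinuation recorded as due to an antipsychotic that starts only after termination | MNAR (Table 4) | Later use is not an event; residual MAR | Caught by MAR sentence | CNSR=3 by default |

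The first three rows are the substantive mismatches. The last two are lesser.

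**Size of a CIR-to-MAR move.** Let δ(t) be the active-minus-placebo benefit at week t. For an active-arm patient whose event is at week t, MAR carries the active increment to week 8 and CIR the placebo increment. The difference is [active(8) − active(t)] − [placebo(8) − placebo(t)] = δ(8) − δ(t). The term for the patient's own earlier residuals cancels. For a placebo patient the two methods coincide. Check: with a linear effect reaching 10 points at week 8 and an event at week 2, δ(2) = 2.5 and the difference is 7.5. A conditional-normal calculation gives the same.

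Arm size: 640/4 = 160 (SAP 2.5, 1:1:1:1 allocation). Shift per patient, as a share of the week-8 effect = [1 − δ(t)/δ(8)]/160. Two onset curves are assumed: linear, and a faster one with δ(t)/δ(8) = (1 − 2^(−t/2))/(1 − 2^(−4)).

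| Event week | Linear: share remaining | Shift | Faster: share remaining | Shift |
|---|---|---|---|---|
| 1 | 87.5% | 0.55% | 68.8% | 0.43% |
| 2 | 75% | 0.47% | 46.7% | 0.29% |
| 4 | 50% | 0.31% | 20% | 0.125% |
| 6 | 25% | 0.16% | 6.7% | 0.04% |

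On an assumed 10-point effect, the week 1 to 4 range is about 0.01 to 0.05 points. At a plateau the shift is 0. If the week-4 effect were 10% above week 8, it would be −0.1/160 = −0.06%. A 5% shift needs 0.05 × 160/0.875 = 9.1, so 10 patients, at the early linear end, and 0.05 × 160/0.20 = 40 at the week-4 faster end, all in one arm.

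This covers moves from CIR to MAR only. A patient with non-oral use who stays on treatment, which Protocol 5.4 leaves to a case-by-case decision, would have no code at all. Read literally, Appendix B would then keep the later measurements. The documents give no figures with which to size that.

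**The case against.** The strongest objection is that this is partly a claim about absent text where text is known to be hidden. The SAP contents list puts 6.2.3 on page 41 and 6.2.4 on page 43, yet only three paragraphs of 6.2.3 are visible. SAP 4.3.1, Protocol 10.3.1 and the Appendix B imputation steps are also not visible. This stands as a limit: hidden text may supply some of the routing. It would not remove the conflict between the two 6.2.3 sentences, add a suicide row to Table 1, or add a declaration to Section 17, all of which can be read.

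A reader might infer stronger points, and the documents do not support them:

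- That disease progression is not assigned to CIR. SAP Table 1 and 6.2.3 assign it by name, and CNSR=1 catches it in part. The fault is loose wording.
- That the SAP contradicts the estimand on every death. Protocol Table 4 names only suicide; other deaths fit its MAR row. The difference is from 10.5.6.1(b), so the protocol is itself unclear.
- That every discontinuation recorded as a need for a prohibited medication is misrouted. For a drug that is not an antipsychotic, MAR agrees with both documents. Antipsychotic use before termination is CIR under Table 1, apart from the declared exception. What remains is an antipsychotic started only after termination.

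There are also safeguards. Protocol 3.2.1 lets the classification be revisited blind, and SAP 5.7 has potential intercurrent events reviewed before unblinding. The tipping-point analysis varies the arms independently, and the treatment-policy analysis does not use this classification. These mitigate but do not state the rule. The case-by-case MAR/MNAR step in SAP 1.2.1 is for events the protocol did not foresee, and suicide was foreseen. The other blinded step there applies Table 1 as it stands.

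**Conclusion.** The point holds in the visible text for three items: suicide falls to MAR undeclared, the antipsychotic code is narrower than Table 1, and the MAR sentence in 6.2.3 overlaps the CIR assignment of disease progression. Non-suicide death and antipsychotics started after termination are lesser clarifications.

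The expected effect is very small: about 0.04% to 0.55% of the treatment effect per active-arm patient moved from CIR to MAR, nil at a plateau. This rests on 160 per arm and on assumed onset curves. The number of affected patients is not in the documents.

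A reader might infer that the primary result is biased towards TV-44749. The documents do not show that: a shift in its favour needs affected active-arm patients and an effect still growing after the event, and the sign reverses if the effect declines. The reason to act is that the primary analysis should follow one stated rule that matches the estimand.

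**What to change.** Before unblinding, put one mapping from discontinuation reason or event, to code, to CIR or MAR into SAP Table 1, 6.2.3 and Appendix B:

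- List suicide, disease progression and discontinuation due to a prohibited antipsychotic under CIR, following Protocol Table 4.
- Reword the MAR sentence in 6.2.3 to cover any reason other than those listed for CIR.
- Remove the oral restriction from CNSR=2 so that it matches Table 1, keeping the short-term oral exception.
- State how non-suicide death is handled.
- If a different classification is intended for any of these, declare and justify it in Section 17.

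Antipsychotic use that merely begins after termination need not become an intercurrent event; only the recorded reason for stopping needs a code. The cost is a few lines of text and code-table wording. The estimate may become very slightly less favourable.

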6.2.4. Primary Analysis

For each of the 200 complete datasets, a mixed model repeated measures (MMRM) analysis will be performed using the change in PANSS score from baseline to week 8 as the dependent variable, and treatment arm, study visit, treatment-by-visit interaction, stratification variables (sex and geographic region), age, and PANSS total score at baseline as covariates. An unstructured covariance matrix will be used in all models. Analyses will be performed in SAS using the Kenward-Roger option to estimate the denominator degrees of freedom and standard errors. If the group size of stratification factors is small, groups may be pooled together for modeling purposes. Such a decision will be made prior to unblinding and documented in the statistical data review meeting.

Least squares means will be calculated of the change from baseline to week 8 in the PANSS total score for each of the 4 treatment arms and for the differences between each of the TV-44749 arms and the placebo arm. In addition, the 95% confidence intervals, and the nominal p-values

for the comparisons between each of the 3 dose strengths of TV-44749 and placebo will be calculated using PROC MIANALYZE using Rubin's rules (see [Appendix B](#) for further details and example code). The nominal p-values will be adjusted for multiplicity (see Section [7](#)).

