10. STATISTICS

This section describes the statistical analysis as foreseen at the time of planning the study. Changes, additions, and further details about the analyses will be described in the statistical analysis plan. After finalization of the statistical analysis plan and unblinding of Period 1, any additional analyses or changes to analyses that may be required will be fully disclosed in the clinical study report (CSR). In the event of any contradiction between the study protocol and the statistical analysis plan, the statistical analysis plan will prevail.

The primary endpoint is change from baseline to week 8 in the PANSS total score. The sample size is designed to detect with [REDACTED] probability a standardized mean difference of [REDACTED] (eg, an improvement of at least [REDACTED] points in the PANSS total score, assuming a standard deviation of [REDACTED] points). The 3 primary efficacy hypotheses will be tested with an overall type I error of 0.05, controlled using truncated Hochberg adjustment for multiplicity.

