10.5.6.1. Primary Efficacy Analysis

[figure not shown]
The efficacy analysis will employ multiple imputation, MMRM, and Rubin's rule.

1. One hundred completed datasets will be imputed using multiple imputation.

- a. For ICEs of a use of prohibited antipsychotic medication or early discontinuation due to insufficient clinical response, imputations will be done assuming MNAR in order to estimate what would have happened if patients who discontinued early had remained in the study on placebo treatment.
- b. For ICEs of early discontinuation due to a reason that is not lack of efficacy or death, a multiple imputation assuming that the clinical effect in these patients is similar to those not experiencing ICE during the study (ie. assuming MAR) will be employed. Full details of the methods employed for the 2 types of ICEs and underlining assumptions will be detailed in the statistical analysis plan.

2. MMRM on change from baseline to week 8: least squares means of change from baseline to week 8, for each of the 4 treatment arms and for the differences between each of the TV-44749 arms to placebo, 95% confidence interval, and p-values will be calculated using MMRM analysis for each complete dataset. The model will include treatment arm, study visit, treatment-visit interaction, stratification variables, and PANSS total score at baseline as covariates. Unless otherwise specified, unstructured covariance matrix will be used as a covariance matrix. Further details about the analysis will be presented in the statistical analysis plan.
3. Summary statistics for the primary efficacy endpoint will be based on Rubin's rule summary of least squares means of change from baseline to week 8, for each of the 4 treatment arms and for the differences between each of the TV-44749 arms to placebo, 95% confidence interval, and p-values. The Rubin's-derived p-values that will be adjusted according to truncated Hochberg method (Section 10.6) will be used for the primary efficacy analysis.

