- Abbreviated physical examination, including weight
- 12-lead ECG
- Vital signs measurement
- Urine β -HCG test for women of childbearing potential
- PANSS
- CGI-S
- AIMS
- BARS
- SAS
- C-SSRS
- PSP
- SQLS
- [REDACTED]
- CDSS
- [REDACTED]
- Abdominal fat measurement (waist-to-hip ratio)
- Blood samples for plasma concentration of IMP
- Blood samples for plasma concentration of IMP at 2.5 to 3 hours postdose
- Blood samples for biomarker analysis
- Blood samples for pharmacogenetics
- Adverse events inquiry (including serious adverse event reporting and injection site related events [including pain])
- Injection site findings and pain assessment
- Inquiry regarding alcohol consumption/illicit drug use
- Cigarette use assessment
- IMP administration
- Concomitant medication inquiry

b. Procedures for Visit 3 (Day 2, Week 0)

The following procedures and assessments will be performed at visit 3:

- Clinical laboratory tests (serum chemistry, hematology, and urinalysis)
- Abbreviated physical examination
- Vital signs measurement
- Blood samples for plasma concentration of IMP
- Adverse events inquiry (including serious adverse event reporting and injection site related events [including pain])
- Injection site findings and pain assessment
- Concomitant medication inquiry

c. Procedures for Visit 4 (Day 8, Week 1), Visit 5 (Day 15, Week 2), Visit 6 (Day 22, Week 3), Visit 8 (Day 36, Week 5), Visit 9 (Day 43, Week 6), and Visit 10 (Day 50, Week 7)

The following procedures and assessments will be performed at visits 4, 5, 6, 8, 9, and 10:

- Vital signs measurement
- PANSS
- CGI-S
- AIMS
- BARS
- SAS
- C-SSRS
- Patient Global Impression-Improvement (PGI-I) (visit 5 only)
- [REDACTED]
- Blood samples for plasma concentration of IMP
- Adverse events inquiry (including serious adverse event reporting and injection site related events [including pain])
- Injection site findings and pain assessment
- Inquiry regarding alcohol consumption/illicit drug use (for outpatients only)
- Concomitant medication inquiry

d. Procedures for Visit 7 (Day 29, Week 4) and Visit 11 (Day 57, Week 8)

The following procedures and assessments will be performed at visits 7 and 11:

- Clinical laboratory tests (serum chemistry, hematology, and urinalysis)
- Thyroid test (visit 11 only)
- Randomization (visit 11 only)

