Randomized patients should have a PANSS total score between 80 and 120, inclusive, at baseline (prior to randomization) with a score ≥ 4 on at least 2 of the following 4 items of the PANSS positive subscale: hallucinatory behavior, delusions, conceptual disorganization, or suspiciousness/persecution.

Patients demonstrating a reduction in the total PANSS score of $\geq 20\%$ between screening and the baseline (randomization) visit will not be eligible for randomization into the study.

Randomized patients will be treated with sc injections of TV-44749 (low [318 mg q1m], medium [425 mg q1m], or high dose [531 mg q1m]) or placebo at visit 2 (week 0) and visit 7 (week 4).

At visits 2 and 7, the PANSS, Columbia Suicide Severity Rating Scale (C-SSRS), CGI-S, and Clinical Global Impression-Improvement (CGI-I; visit 7 [week 4] only) scales should be completed prior to investigational medicinal product (IMP) administration; all other scales and questionnaires may be completed either prior to IMP administration or after. Any assessments performed after IMP administration must be completed on the day of IMP administration.

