6.4.1.2. Analysis

MMRM model will be repeated for this endpoint

```
proc mixed data=data method=reml;
  class trt01pn avisitn subjid;
  model variable = trt01pn avisitn trt01pn*avisitn sex region age
baseline/ddfm=kr cl;
  repeated avisitn/subject=subjid type=un;
  lsmeans trt01pn*avisitn/cl;
run;
```

Results Presentation

Summary statistics will be produced for absolute and change from period 2 baseline, by timepoint and treatment (TV-44749 318mg, TV-44749 425mg, TV-44749 531mg and former placebo assignment, i.e., overall 6 groups for period 2)

Least-square means of absolute value and change from baseline, including standard errors and 95% CI, will be presented at each timepoint by treatment group.

6.4.2. Clinical Global Impression-Severity (CGI-S) – Change From Baseline to End of Treatment Period in Period 2

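### The primary MMRM has no baseline-by-visit term; adding one before unblinding is a free and probably small gain in Week 8 precision

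*SAP*

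**What the plan says.** SAP Section 6.2.4 gives the fixed effects as "treatment arm, study visit, treatment-by-visit interaction, stratification variables (sex and geographic region), age, and PANSS total score at baseline as covariates". Protocol Section 10.5.6.1 has the same structure without age: "The model will include treatment arm, study visit, treatment-visit interaction, stratification variables, and PANSS total score at baseline as covariates". On the covariance, the SAP states: "An unstructured covariance matrix will be used in all models". The model is fitted to imputed data: "For each of the 200 complete datasets, a mixed model repeated measures (MMRM) analysis will be performed".

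PANSS is rated weekly. Protocol Appendix B introduces one list that includes PANSS with "The following procedures and assessments will be performed at visits 4, 5, 6, 8, 9, and 10", and a second list covers visits 7 and 11, which makes eight post-baseline ratings. Only the Week 8 contrast is the primary test.

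The by-visit PANSS model in SAP 6.3.3 also carries baseline as a main effect. So does the one piece of model code that can be read, for Period 2 in SAP 6.4.1.2: "model variable = trt01pn avisitn trt01pn*avisitn sex region age", followed by baseline and no baseline-by-visit product. The two key secondary endpoints (SAP 6.3.1.2 and 6.3.2.2) follow the steps of 6.2.4 with the outcome changed.

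**The concern.** With treatment crossed with visit and baseline not, the model assumes that a one-point difference in baseline PANSS predicts the same difference in change at Week 1 as at Week 8. Under an unstructured covariance the single slope is a precision-weighted average over visits. If residual variance rises over time and successive visits are strongly correlated, nearly all the weight falls on the earliest visit. Chance imbalance in baseline between arms is then corrected at Week 8 with a slope that may not be the Week 8 slope.

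At stake is efficiency in the three dose-versus-placebo tests, and in the CGI-S analysis that follows the same steps. No other property of the analysis is in question.

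**Working it through.** **What the plan gives.** It states no figure for the precision gained from baseline adjustment, so there is none to reproduce. The sample size is about 440 completers and 640 randomized; 440/640 = 0.6875 implies about 31% early termination. It cannot be rebuilt, because the effect size, power and termination rate are blacked out, and Protocol Section 10 has "assuming a standard deviation of" before a redacted value. The slopes, baseline SD and between-visit correlations are not given. Every input below is therefore an assumption, with slopes and residual SDs moving linearly from Week 1 to Week 8.

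**Formulas (complete data).** Let β_t be the slope of change on baseline at visit t, S the residual covariance, SD_x the baseline SD and SD_8 the Week 8 residual SD.

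- Common slope: b = (1′S⁻¹β)/(1′S⁻¹1).
- Week 8 contrast variance relative to visit-specific slopes: 1 + (β_8 − b)²·SD_x²/SD_8².
- The same ratio with no baseline covariate: 1 + β_8²·SD_x²/SD_8².
- Share of the adjustment gain lost: (first ratio − 1)/(second ratio − 1).

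**Worked example.** Take SD_x 10, residual SD 8 rising to 18, AR(1) correlation 0.9 and slopes from −0.1 to −0.4. The weights on the eight visits are 1.220, −0.120, −0.061, −0.032, −0.017, −0.009, −0.004 and 0.023, so Week 1 dominates and Week 8 carries about 2%. This gives b = −0.086.

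- Common slope: 1 + (0.314)²·100/324 = 1.030.
- No adjustment: 1 + 0.16·100/324 = 1.049.
- Share lost: about 61%.

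A simulation of 1,500 trials with 160 per arm gave 1.033 and 1.052. The model-based variance was within 1% of the empirical variance.

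| SD_x | Residual SD | AR(1) | Slopes, Week 1 to 8 | b | Ratio, common slope | Ratio, no baseline | Share lost |
|---|---|---|---|---|---|---|---|
| 9 | 8–18 | 0.8 | −0.2 to −0.3 | −0.212 | 1.002 | 1.023 | 9% |
| 9 | 8–18 | 0.9 | −0.2 to −0.3 | −0.195 | 1.003 | 1.023 | 12% |
| 9 | 8–20 | 0.8 | −0.1 to −0.4 | −0.126 | 1.015 | 1.032 | 47% |
| 9 | 8–20 | 0.9 | −0.1 to −0.4 | −0.078 | 1.021 | 1.032 | 65% |
| 9 | 8–20 | 0.9 | 0 to −0.3 | +0.022 | 1.021 | 1.018 | 116% |
| 10 | 8–18 | 0.95 | −0.05 to −0.5 | +0.059 | 1.097 | 1.077 | 125% |

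A share above 100% means the common-slope model does slightly worse than no baseline covariate. If the slopes are constant, β_8 = b and nothing is lost.

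**Wider grid.** 504 scenarios were run: baseline SD 7 to 11.5 (a uniform spread over 80–120 gives 40/√12 = 11.5), Week 1 slope 0 to −0.2, Week 8 slope −0.3 to −0.7, and AR(1) 0.8–0.9 or exchangeable 0.6–0.75. The median SE inflation was 1.3%, the middle half 0.5% to 2.9%, and the 90th percentile about 5%. One extreme corner reached 19% (slopes −0.05 to −0.7, exchangeable 0.75, baseline SD 11.5).

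**In power terms.** At an assumed planned power of 80–90%, a 0.5% SE inflation costs about 0.3 to 0.5 points and a 2% inflation about 1.2 to 1.8 points per comparison. A variance ratio of 1.021 corresponds to 640·(1 − 1/1.021) ≈ 13 patients.

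**PSP.** Period 1 has only two post-baseline ratings, at Weeks 4 and 8. With assumed slopes −0.3 and −0.4, baseline SD 10, residual SD 11 and 13, and correlation 0.6–0.8, the variance loss is 0.3–0.5%, or 3–5% of the gain.

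**The case against.** The strongest reply is that the stake is small and rests on inputs from outside the documents. The outcome is already a change from baseline, and entry restricts baseline PANSS to 80–120, so even the best adjustment gains little: 4.9% of variance in the worked example. Nothing in the documents says that the slope grows between Week 1 and Week 8; with slopes of −0.2 to −0.3 the loss is 0.2–0.3% of variance. All of this stands, and it limits the claim to a modest one.

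Three further points narrow it:

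- The formulas assume complete data, whereas the plan pools 200 imputed datasets by Rubin's rules with about 31% early termination. The between-imputation variance is left out, so the patient equivalent is only illustrative.
- The Appendix B analysis-model code cannot be read, and it might contain the term.
- The early-visit mechanism does not carry over to PSP.

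Two points do not remove the case. The protocol records 675 randomized by 29 January 2024, 35 above plan, and SAP 6.1 says that the option to enroll without placebo was not used. That surplus may offset a loss of this size, but it does not make the less precise model preferable. A further SAP edit after Amendment 01, which answered regulatory comments, is an administrative cost; SAP 2.6.2 provides for changes before unblinding.

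**Conclusion.** On the visible text the structural point holds: one baseline slope is shared by eight visits in the primary model. If that slope differs between early visits and Week 8, the Week 8 variance is about 0.2–10% larger than it need be, typically 1–4%, or about 0.5–2% of the SE. This range rests on assumed baseline SD 8–10, residual SD 8 rising to about 18–20, AR(1) correlation 0.80–0.95 and Week 8 slopes of about −0.25 to −0.50. More extreme inputs give more, and constant slopes give zero.

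A reader might infer that the model throws away most of the benefit of baseline adjustment. The documents do not support that as a general statement. The share lost runs from about a tenth to over the whole in the scenarios above, it depends on slopes that are nowhere stated, and it is a share of a small gain. Nor do they support reading this as bias, inflated type I error or a conflict between protocol and SAP. Randomization protects the contrast, the estimated covariance absorbs the misfit, and both documents enter baseline in the same way. Confidence is high on the structure and low on the size.

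**What to change.** Before unblinding:

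- Add baseline PANSS-by-visit to the models in SAP 6.2.4 and 6.3.3.
- Add baseline CGI-S-by-visit to the CGI-S model. Section 6.3.1.2 changes only the outcome, so the baseline covariate should be named there as well.
- Use the same form for PSP for consistency, with little gain expected.
- If the Appendix B code already contains the term, align the text of 6.2.4 with it. If the term is left out on purpose, give the reason.

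The statistical cost is 7 degrees of freedom for an eight-visit endpoint (eight slopes instead of one) and 1 for PSP, among about 640 patients. No estimand, visit, assessment or patient-level procedure changes. The remaining cost is one documented SAP edit.
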